5.6.2 Duration of Complete Response (DoCR)

DoCR will be evaluated only in the set of participants who are in CR at Day 28 post-randomization. The primary definition of DoCR is the time from Day 28 until an aGVHD target organ worsens by at least 1 stage and requires a significant escalation in treatment (defined below), or death. The transient worsening of symptoms that resolve without significant escalation of treatment is not considered a loss of CR. A significant escalation in treatment is defined as initiation of new systemic treatment for GVHD and/or escalation in methylprednisolone dose (or equivalent). Methylprednisolone dose increases must be greater than 25% of the current dose and increase at least 8 mg/day (or other steroid equivalent) to be considered an escalation of methylprednisolone. DoCR will be described for each arm using the Kaplan-Meier estimator, with estimates and 95% CIs for the median of DoCR obtained from this estimator using the method described in Andersen et al. 1993, Chapter IV.

A Cox proportional hazards model will compare the hazard rates of loss of CR between the T-Guard and ruxolitinib arms through Day 180 while adjusting for the stratification factors. This will include DoCR events as defined in the previous paragraph.

A secondary analysis will use an alternative definition of DoCR as the time from Day 28 until death or a significant escalation of aGVHD therapy occurs, as defined in the primary analysis of DoCR. DoCR defined in this manner will be described for each arm using the Kaplan-Meier estimator, with estimates and 95% CIs for the median of DoCR obtained from this estimator using the method described in Andersen et al. 1993, Chapter IV.

Other Secondary Endpoints:

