3 STUDY ENDPOINTS

3.1 ACUTE GVHD RESPONSE DEFINITIONS

Scoring of aGVHD response on a given day is in comparison to the participant's aGVHD staging on the day of randomization. Organ staging will be assessed using the MAGIC criteria (see APPENDIX C) and response will be scored as defined below:

Complete response (CR) is defined as a score of 0 for the GVHD staging in all evaluable organs. For example, for a response to be scored as CR, the participant must still be in CR on that day and have had no intervening additional systemic therapy for treatment of aGVHD.

Partial response (PR) is defined as improvement in one or more organs involved with GVHD symptoms without progression in others. For example, for a response to be scored as PR, the participant must still be in PR on that day and have had no intervening additional systemic therapy for treatment of aGVHD.

Mixed response (MR) is defined as improvement in one or more organs with deterioration in another organ manifesting symptoms of GVHD or development of symptoms of GVHD in a new organ.

No response (NR) is defined as absence of any improvement or progression as defined. Participants receiving additional systemic therapy will be classified as non-responders.

Progression is defined as deterioration in at least one organ without any improvement in others.

Loss of CR is defined as progression of aGVHD symptoms requiring additional systemic therapy (including escalation of corticosteroid dose to or beyond 2mg/kg methylprednisolone (or equivalent)); death; or if the participant develops new target organ symptoms that could qualify as being from either aGVHD or cGVHD (if the new symptoms are only associated with cGVHD then this is not considered a loss of CR).

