3.4.1.2 Duration of Complete Response (DoCR)

DoCR is defined as the time from Day 28 until an aGVHD target organ worsens by at least 1 stage and requires a significant escalation in treatment (defined below), or death. The transient worsening of symptoms that resolve without significant escalation of treatment is not considered a loss of CR. A significant escalation in treatment is defined as initiation of new systemic treatment for GVHD and/or escalation in methylprednisolone dose (or equivalent).

Methylprednisolone dose increases must be greater than 25% of the current dose and increase at least 8 mg/day (or other steroid equivalent) to be considered an escalation of methylprednisolone. DoCR will be evaluated in the set of participants who are in CR on Day 28 after randomization.

3.4.2 Other Secondary Endpoints:

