5.1.2 Randomization and Blinding

Participants will be randomized at the time of enrollment in a 1:1 ratio to the treatment arms. Randomization will be stratified by center region (US vs. Europe) and age group (at least 55 years vs. under 55). Stratified treatment assignments will be generated using permuted blocks of random sizes.

As this is an open-label trial, no blinding will be performed.

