5.6 ANALYSIS OF SECONDARY ENDPOINTS

The analysis of secondary endpoints will be based on the primary ITT analysis population. A supplemental analysis will also be performed in the PP population.

Key Secondary Endpoints:

The study has two key secondary endpoints: OS and DoCR. The comparison of OS between treatment arms will be alpha-protected; to protect the familywise type I error rate of 2.5%, a gatekeeping procedure will be employed where OS will be tested for superiority of T-Guard to ruxolitinib only if a significant benefit of T-Guard is found in the pivotal analysis of the primary endpoint.

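### The duration-of-CR hazard ratio is estimated only among Day 28 complete responders, so it is not a randomized comparison; it can mislead in either direction and needs an all-randomized comparison beside it

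*Combined protocol and SAP*

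**What the plan says.** Section 5.6 names OS and DoCR as the key secondary endpoints and sets the general rule: "The analysis of secondary endpoints will be based on the primary ITT analysis population". DoCR departs from that rule in both places where it is specified. Section 3.4.1.2 has "DoCR will be evaluated in the set of participants who are in CR on Day 28 after randomization" and section 5.6.2 has "DoCR will be evaluated only in the set of participants who are in CR at Day 28 post-randomization".

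Section 5.6.2 then goes beyond description: "A Cox proportional hazards model will compare the hazard rates of loss of CR between the T-Guard and ruxolitinib arms". The specification continues: "arms through Day 180 while adjusting for the stratification factors. This will include DoCR events as defined in the previous paragraph". The stratification factors are given in section 5.1.2: "Randomization will be stratified by center region (US vs. Europe) and age group (at least 55 years vs. under 55". Grade III vs. IV is not one of them.

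On multiplicity, section 5.6 protects only the OS comparison, through a gate on the primary endpoint. Nothing comparable is stated for DoCR.

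The term loss of CR is worded in two ways. Section 3.1 has "Loss of CR is defined as progression of aGVHD symptoms requiring additional systemic therapy (including escalation of corticosteroid dose to or beyond 2mg/kg methylprednisolone", and also counts death and new target-organ symptoms that might be acute or chronic GVHD, while exempting symptoms that are purely chronic. Sections 3.4.1.2 and 5.6.2 require a one-stage organ worsening together with new systemic treatment or a steroid increase, or else death. For steroids, "Methylprednisolone dose increases must be greater than 25% of the current dose and increase at least 8 mg/day".

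**The concern.** Randomization makes the two arms alike at entry. It does not make the responders in one arm like the responders in the other, because being a responder is itself a result of treatment. If T-Guard raises the CR rate as planned, its responder set includes people who would not have responded to ruxolitinib and who have no counterpart in the other arm. Any difference between them and the remaining responders in their tendency to lose CR enters the hazard ratio as if it were a drug effect on durability.

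At stake is how a key secondary result will be read in a trial meant to support FDA and EMA applications. A drug that produces more lasting complete responses could show an unfavorable DoCR hazard ratio, or a favorable one could owe nothing to durability.

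The missing grade covariate is a separate and smaller matter. It leaves a named baseline factor unadjusted in the one comparison that randomization does not balance.

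**Working it through.** **Inputs from the documents.** Day 28 CR rates of 43% and 26% and a total of 246 (section 5.1.5); 1:1 allocation (section 5.1.2), so 123 per arm; DoCR runs from Day 28 to Day 180, or 180 − 28 = 152 days (section 5.6.2).

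**The plan's own figure.** The plan gives no sample size, event count or power for DoCR. Its primary-endpoint figures do reproduce. A fixed design needs 122 per arm (244 in total) for 80% power at one-sided 2.5%. Simulation with the stated boundaries and futility rule, using an unpooled Z statistic, gives 80.5% power and 2.35% type I error, against 80.56% and 2.37% in Table 5-2.

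**Who enters the DoCR model.** T-Guard: 0.43 × 123 = 53. Ruxolitinib: 0.26 × 123 = 32. Together that is about 85 of 246 randomized.

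**Assumptions for the illustration (none is a document figure).**
1. Monotonic response: everyone who would reach CR on ruxolitinib would also reach it on T-Guard. Per 100 randomized to T-Guard there are then 26 shared and 17 extra responders, so 17/43 = 40% of T-Guard responders have no ruxolitinib counterpart.
2. The drug has no effect on durability.
3. Shared responders lose CR at a constant hazard, with 30% lost by Day 180.
4. Extra responders lose CR at k times that hazard.

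**Calculation.** Among ruxolitinib responders the hazard is the base hazard throughout. In the T-Guard responder set, the hazard relative to base is:
- at Day 28: (26 + 17k)/43;
- at Day 180: (26 × 0.70 + 17 × k × 0.70^k)/(26 × 0.70 + 17 × 0.70^k).

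The Cox estimate is an average over the period and lies between these two. Solving the large-sample Cox score equation gives the fourth column. The last column repeats it with 10% and with 50% loss in shared responders.

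| k | Ratio at Day 28 | Ratio at Day 180 | Expected Cox HR, 30% loss | HR at 10% / 50% loss |
|---|---|---|---|---|
| 0.5 | 34.5/43 = 0.80 | 25.31/32.42 = 0.78 | 0.79 | 0.80 / 0.78 |
| 1 | 1.00 | 1.00 | 1.00 | 1.00 / 1.00 |
| 1.5 | 51.5/43 = 1.20 | 33.13/28.16 = 1.18 | 1.19 | 1.20 / 1.18 |
| 2 | 60/43 = 1.40 | 34.86/26.53 = 1.31 | 1.36 | 1.38 / 1.33 |
| 3 | 77/43 = 1.79 | 35.69/24.03 = 1.49 | 1.64 | 1.74 / 1.54 |

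The true effect on durability is nil in every row, so only k = 1 returns the right answer.

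**What the same scenario looks like in all randomized participants.** At k = 2, CR at Day 28 maintained to Day 180 is 0.26 × 0.70 + 0.17 × 0.49 = 26.5% on T-Guard and 0.26 × 0.70 = 18.2% on ruxolitinib. T-Guard yields 8 points more durable responses while the responder-only hazard ratio reads 1.36 against it.

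**Covariates.** The adjusted comparisons in sections 5.5, 5.6.1, 5.6.3, 5.6.4, 5.6.6 to 5.6.10 and 5.6.12 all include grade III vs. IV. Section 5.6.2 alone does not, and it gives no reason.

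**The case against.** The other side has several fair points.

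- **Status of the endpoint.** DoCR carries no alpha and no success claim, and duration of response exists only in responders. This stands. It lowers the stakes, but it does not turn the between-arm hazard ratio into a randomized comparison.
- **All-randomized counterparts exist.** OS is compared in everyone. GVHD-free survival (section 5.6.8) is compared at Day 180 with grade adjustment, and it requires CR, which section 3.1 scores only without intervening systemic therapy. This stands in part. GVHD-free survival also admits a CR first reached after Day 28 and counts chronic GVHD as failure, so it does not measure how long a Day 28 CR lasts.
- **The shift is within the noise.** At 30% loss there are about 0.30 × 85 = 25 events. With a 53:32 split (0.62 and 0.38), the standard error of the log hazard ratio is 1/√(25 × 0.62 × 0.38) = 0.41, so a 95% interval around 1 runs from about 0.45 to 2.25. That is true of a single trial, but bias does not average out, and the point estimate will still be reported.
- **Durable CR is a different quantity.** It mixes response with durability, as the 26.5% vs. 18.2% example shows. This stands, so it should supplement DoCR and not replace it.

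A reader might also infer more than the documents support:
- That the bias runs against T-Guard because its extra responders are harder to treat. The documents establish neither monotonic response nor a higher loss hazard in the extra responders; a lower hazard flatters T-Guard.
- That the missing grade covariate or the two loss-of-CR wordings make the comparison non-randomized. Only the responder restriction does that, and adding grade would not restore randomization.
- That the section 3.1 wording leaves the Cox event undefined. Section 5.6.2 ties the model to its own DoCR definition.

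**Conclusion.** The concern holds in this form: the DoCR hazard ratio conditions on Day 28 CR, a post-randomization outcome that treatment is expected to move from 26% to 43%, and so it is not a randomized estimate of an effect on durability. That conclusion follows from the plan's text alone. Its numerical size does not: the 0.79 to 1.64 range rests wholly on the assumptions listed above, and neither direction nor magnitude can be known in advance.

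The omission of aGVHD grade is a separate inconsistency with every other adjusted comparison in sections 5.5 and 5.6. The differing loss-of-CR wording is a minor matter of reconciliation. Because DoCR is not alpha-protected, the change is one the sponsor should make; the primary analysis and the OS gate are untouched.

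**What to change.** 1. In section 5.6.2, keep the responder-only Kaplan-Meier curves and medians. State that any responder-only Cox hazard ratio is descriptive and non-randomized.
2. Add aGVHD grade at randomization (III vs. IV) to that model, in line with the rest of sections 5.5 and 5.6.
3. Add a supportive comparison in all randomized participants: durable CR, meaning CR at Day 28 with no DoCR event through Day 90 and, as a second time point, through Day 180, with everyone else counted as a failure. Use logistic regression adjusted for region, age and grade. Say in the text that this combines response and durability and does not isolate durability.
4. Reconcile the loss-of-CR wording in section 3.1 with sections 3.4.1.2 and 5.6.2, including how symptoms attributable only to chronic GVHD are handled. Simply overwriting section 3.1 would delete its exemption for those symptoms, which the other two sections do not state.

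The cost is SAP wording and one extra model at two time points. Section 4.3.2 already schedules aGVHD staging at Days 28, 35, 42, 49, 56, 70, 90 and 180 and records every corticosteroid dose change, so no new data are needed. The sponsor gives up presenting the responder-only hazard ratio as a treatment comparison.

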5.6.3 Time to Complete Response (CR)

The time from randomization until first attaining a CR will be described for each treatment arm using the Aalen-Johansen estimator, with death and additional systemic treatment for aGVHD treated as competing risks. Estimates and 95% CIs of the cumulative incidence of CR will be

provided at Days 28 and 56 post-randomization. The cause-specific hazards of CR will be compared between arms using a Cox proportional hazards model with adjustment for the stratification factors and for acute GVHD grade at randomization (Grade III vs. IV).

5.6.4 Overall Response Rate (ORR)

Overall response is defined as either a complete or participant response (CR+PR). The ORR will be estimated at Days 14, 28, and 56 post-randomization for each treatment arm using sample proportions and 95% Wilson score or Clopper-Pearson CIs, as appropriate. ORRs will be compared between arms by evaluating the odds ratio of CR/PR for T-Guard vs. ruxolitinib using logistic regression with adjustment for the stratification factors and for acute GVHD grade at randomization (Grade III vs. IV).

5.6.5 Proportion of Response

The proportion of participants in each aGVHD response category will be described at Days 6 14, 28 and 56 post-randomization for each treatment arm. These proportions will be compared between arms using Pearson's chi-square test or Fisher's exact test as appropriate.

5.6.6 Non-relapse Mortality (NRM)

NRM is defined as death from any cause other than malignancy relapse/progression. The time from randomization until NRM will be described for each treatment arm using the Aalen-Johansen estimator, with malignancy relapse/progression treated as a competing risk. Estimates and 95% CIs of the cumulative incidence of NRM will be provided at Days 100 and 180 post-randomization. The cause-specific hazards of NRM will be compared between arms using a Cox proportional hazards model with adjustment for the stratification factors and for acute GVHD grade at randomization (Grade III vs. IV).

5.6.7 Relapse-free Survival (RFS)

RFS is defined as being alive and free of malignancy relapse/progression. The time from randomization until malignancy relapse/progression or death will be described for each arm using the Kaplan-Meier estimator. Estimates and 95% CI for RFS at Day 180 post-randomization will be provided. A Cox proportional hazards model will compare the hazard rates of relapse/progression/mortality between the T-Guard and ruxolitinib arms with adjustment for the stratification factors and for acute GVHD grade at randomization (Grade III vs. IV).

5.6.8 GVHD-free Survival

GVHD-free survival is defined as being alive, in CR, and free of cGVHD. The proportion of participants with GVHD-free survival at Days 90 and 180 post-randomization will be estimated for each treatment arm using sample proportions and 95% Wilson score or Clopper-Pearson CIs, as appropriate. The proportions of participants with GVHD-free survival at Day 180 will be compared between arms using logistic regression with adjustment for the stratification factors and for acute GVHD grade at randomization (Grade III vs. IV).

5.6.9 Chronic GVHD (cGVHD)

cGVHD severity is defined per the 2014 NIH Consensus Criteria (see APPENDIX D). The maximum severity of cGVHD through Day 180 post-randomization will be tabulated by arm. The time from randomization until onset of cGVHD of any severity (mild, moderate, or severe) will be described for each treatment arm using the Aalen-Johansen estimator, with death prior to cGVHD onset treated as a competing risk. Estimates and 95% CIs of the cumulative incidence of cGVHD will be provided at Day 180 post-randomization. The cause-specific hazards of cGVHD will be compared between arms using a Cox proportional hazards model with adjustment for the stratification factors and for acute GVHD grade at randomization (Grade III vs. IV).

5.6.10 Relapse/Progression of Underlying Malignancy

The time from randomization until malignancy relapse/progression will be described for each treatment arm using the Aalen-Johansen estimator, with death prior to relapse/progression treated as a competing risk. Estimates and 95% CIs of the cumulative incidence of malignancy relapse/progression will be provided at Day 180 post-randomization. The cause-specific hazards of relapse/progression will be compared between arms using a Cox proportional hazards model with adjustment for the stratification factors and for acute GVHD grade at randomization (Grade III vs. IV).

5.6.11 Incidence of Infections

The frequency of Grade 2-3 infections occurring from randomization until Day 90 post-randomization will be tabulated by infection site, date of onset, and severity, with Grade defined per Appendix G. Grade 1 CMV infections requiring treatment that occur post-randomization will also be summarized. The cumulative incidence of Grade 2-3 infections at Day 90 post-randomization will be described by treatment arm using the Aalen-Johansen estimator and its 95% CI, with death prior to infection treated as a competing risk. The cumulative incidence of treated CMV will similarly be estimated at Day 90 for each arm.

5.6.12 Incidence of Toxicities

The frequency of Grade 3-5 toxicities per CTCAE Version 5 occurring from randomization until 56 days post-randomization will be tabulated by organ system for each treatment arm. The maximum severity of reported toxicities during that period will also be summarized. The proportions of participants reporting Grade 3-5 toxicities through Day 56 will be compared between arms using logistic regression with adjustment for the stratification factors and for acute GVHD grade at randomization (Grade III vs. IV).

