19. Patients who have a BMI greater than or equal to 35 kg/m².
20. Patients who are taking sirolimus must have it discontinued prior to starting study treatment.
21. Female patients who are pregnant, breast feeding, or, if sexually active and of childbearing potential, unwilling to use effective birth control from start of treatment until 30 days after the last treatment dose.
22. Male patients who are, if sexually active and with a female partner of childbearing potential, unwilling to use effective birth control from start of treatment until 65 days after the last treatment dose.
23. Patients with any condition that would, in the investigator's judgment, interfere with full participation in the study, including administration of study drug and attending

required study visits; pose a significant risk to the patient; or interfere with interpretation of study data.

24. Patients whose decision to participate might be unduly influenced by perceived expectation of gain or harm by participation, such as patients in detention due to official or legal order.

Interim Analysis:

This trial will include one interim analysis for futility after 23 participants on the T-Guard arm (~46 participants total) become evaluable for the primary endpoint. One interim analysis for efficacy will be performed once 150 participants on combined arms have reached Day 28 and 100 participants on the combined arms have reached Day 180.

Treatment Description:

Participants will be randomized to receive either T-Guard or ruxolitinib. Participants on the T-Guard arm will receive 4 doses of T-Guard treatment, administered intravenously as four 4-hour infusions at least two calendar days apart. Each dose consists of 4 mg/m² Body Surface Area (BSA). Participants on the ruxolitinib arm will receive 10mg orally of ruxolitinib twice daily for a planned minimal period of 56 days.

Accrual Objective:

The target accrual is 246 participants randomized 1:1 between the treatment arms from approximately 75 transplant centers in the US and Europe.

Accrual Period:

Approximately 34 months is expected for accrual.

Study Duration:

Participants will be followed for 180 days after randomization for a total study duration of approximately 40 months.

Safety Monitoring:

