1.3.2.1 Clinical Data

Because clinical trials are conducted under widely varying conditions, adverse reaction rates observed in the clinical trials of a drug cannot be directly compared to rates in the clinical trials of another drug and may not reflect the rates observed in practice.

The safety of ruxolitinib was assessed in 617 patients in six clinical studies with a median duration of follow-up of 10.9 months, including 301 patients with myelofibrosis in two Phase 3 studies.

In these myelofibrosis studies, patients had a median duration of exposure to ruxolitinib of 9.5 months (range 0.5 to 17 months), with 88.7% of patients treated for more than 6 months and 24.6% treated for more than 12 months. One hundred and eleven (111) patients started treatment at 15 mg twice daily and 190 patients started at 20 mg twice daily. In patients starting treatment with 15 mg twice daily (pretreatment platelet counts of 100 to 200 x 10⁹/L) and 20 mg twice daily (pretreatment platelet counts greater than 200 x 10⁹/L), 65% and 25% of patients,

respectively, required a dose reduction below the starting dose within the first 8 weeks of therapy.

In the SR-aGVHD setting, a multicenter, randomized, open-label Phase 3 study of ruxolitinib versus BAT was performed (REACH2). Of the 154 patients assigned to the ruxolitinib arm, 152 were treated with ruxolitinib, of the 155 patients assigned to the control arm, 150 patients received BAT.

The most common adverse events up to day 28 were thrombocytopenia (in 50 of 152 patients [33%] receiving ruxolitinib and 27 of 150 [18%] patients receiving the control), anemia (in 46 [30%] and 42 [28%], respectively), and CMV infection (in 39 [26%] and 31 [21%]) (Zeiser, Bubnoff et al. 2020).

Treatment discontinuation occurred in 111 of 154 patients (72%) assigned to ruxolitinib and in 132 of 155 (85%) assigned to the control; the most common reason was lack of efficacy (in 32 [21%] and 68 [44%], respectively). The median duration of exposure to therapy was 63 days (range, 6 to 396) in the ruxolitinib group and 29 days (range, 1 to 188) in the control group. The median dose intensity of ruxolitinib was 16.8 mg per day (interquartile range, 11.9 to 19.6).

[Table 1-3](#) presents the most common adverse reactions occurring in the 152 patients who received ruxolitinib and the 150 patients treated with the control in the randomized REACH2 study.

Table 1-3: Most Frequent Adverse Events up to Day 28 (Safety Population)*

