2.5.2.3 Dose and Administration of Ruxolitinib

Participants randomized to the ruxolitinib arm will receive 10mg orally twice daily to begin on Day 0. Dose modifications for toxicity are described below. Participants responding to treatment may be tapered off ruxolitinib as needed, starting no earlier than Day 56. The dose tapering strategy should be based on evaluation of the condition of the participant, current dosing regimen and the clinical judgment of the Investigator.

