3.4.2.10 Incidence of Toxicities

All Grade 3-5 toxicities according to CTCAE v5 occurring from randomization to Day 56 post-randomization will be described.

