Pre-infusion samples should be drawn prior to T-Guard administration. A window of +/- 15 minutes is allowed for samples drawn at 4 hours after the start of infusion, a window of +/-30 minutes for the sample drawn 5, 6, or 8 hours after the start of infusion, and a window of +/- 1 hour for samples drawn 24 or 48 hours after the start of infusion. Every effort should be made to collect PK samples at all timepoints; however, *no* PK sampling is required on weekend days. Please refer to Section 2.5.1.5 for more information regarding T-Guard infusion delays.

Post-Randomization Assessments

The following assessments and observations must be completed at the timepoints designated below.

1. Complete aGVHD staging and grading information including assessments of rash, diarrhea, nausea/vomiting, and bilirubin at Days 0, 6, 14, 21, 28, 35, 42, 49, 56, 70, 90, and 180
2. cGVHD evaluation (if present) Day 28, 56, 90, and 180
3. Blood pressure at Days 0, 6, 14, 21, 28, 35, 42, 49, 56, 70, 90, and 180
4. Albumin at Days 0, 6, 28, 56, 90, and 180
5. CBC with differential and platelets at Days 0, 6, 14, 21, 28, 56, 90, and 180
6. Renal function (blood urea and/or blood urea nitrogen, creatinine) on Days 6, 14, 21 and 28
7. Schistocytes, haptoglobin and LDH on Days 6, 14, 21 and 28
8. Karnofsky performance status at Days 28, 56, 90, and 180
9. Peripheral blood for EBV and CMV viral load at Days 6, 14, 21, 28, 35, 42, 49, 56 and 180
10. Recording and review of Concomitant medications other than immunosuppressant agents will be collected starting at 7 days prior to randomization through 30 days post-last treatment dose for T-Guard and through Day 44 for ruxolitinib. Recording of all systemic immune suppressive therapy (as appropriate: tacrolimus, cyclosporine, etc.), as well as topical agents, and all anti-infectives used for prophylaxis or treatment at Days 6,

14, 21, 28, 35, 42, 49, 56, 70, 90, and 180

- a. For all immunosuppressant agents, the overall start and stop date will be captured. For agents where dosing is tapered in response to drug levels, the medication dosing will not require reporting.
- b. Dosing for corticosteroids will be captured for all dosing changes.

11. Patient reported outcomes at Days 28, 90 and 180 (see APPENDIX E)

12. Recording of toxicities on Days 56, 70, 90, and 180

13. Recording of AE/SAEs as described in Section 4.4 Adverse Event Reporting

14. Recording of infections through Day 180

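### Toxicities are recorded to Day 180, but the only specified toxicity summary by arm stops at Day 56, the planned minimum ruxolitinib period

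*Combined protocol and SAP*

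**What the plan says.** The endpoint definition in section 3.4.2.10 reads: "All Grade 3-5 toxicities according to CTCAE v5 occurring from randomization to Day 56 post-randomization will be described". Section 5.6.12 uses the same window for the tabulation ("The frequency of Grade 3-5 toxicities per CTCAE Version 5 occurring from randomization until 56 days post-randomization") and for the test: "The proportions of participants reporting Grade 3-5 toxicities through Day 56 will be compared between arms using logistic regression", adjusted for the stratification factors and aGVHD grade.

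The assessment list in section 4.3.2 runs longer: "Recording of toxicities on Days 56, 70, 90, and 180". The matching objective in section 2.3.2, to describe the incidence of toxicities, carries no Day 56 limit.

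On exposure, the synopsis gives the control arm "10mg orally of ruxolitinib twice daily for a planned minimal period of 56 days", and section 2.5.2.3 states: "Participants responding to treatment may be tapered off ruxolitinib as needed, starting no earlier than Day 56". Section 2.5.2.2 makes supply arrangements for participants who continue past Day 56. T-Guard must be finished within 14 days of its first dose (section 2.5.1.7), and treatment must start within 72 hours of randomization (section 2.5). For the earlier randomized phase 3 trial of ruxolitinib, section 1.3.2.1 reports: "The median duration of exposure to therapy was 63 days (range, 6 to 396) in the ruxolitinib group".

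**The concern.** Data are collected on a schedule that the analysis does not use, and the plan gives no reason for either the cut-off or the later forms. The arms are also truncated differently. After Day 56 every T-Guard participant is well past dosing, while a ruxolitinib participant may be on full dose, tapering or off drug. The background (section 1.2.3) presents the lack of ongoing exposure to immunosuppressive agents as an advantage of T-Guard, so toxicity during longer ruxolitinib treatment belongs to the benefit-risk comparison. Table 1-3 shows that this toxicity is not trivial: by Day 28 in the earlier trial, Grade 3 or higher thrombocytopenia was 27%, anemia 22% and neutropenia 13% on ruxolitinib.

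At stake is the completeness of the safety comparison, and whether any later toxicity table is specified in advance or chosen after the data are seen, in an open-label trial meant to support FDA and EMA applications. The primary endpoint, alpha and sample size are not affected.

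**Working it through.** The plan has no figure to reproduce here. The check sets the recording schedule against the analysis window and then sizes the gap.

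**1. Schedule against window.** Recordings fall on Days 56, 70, 90 and 180 (section 4.3.2); the analysis ends at Day 56 (sections 3.4.2.10 and 5.6.12).
- Recordings after the cut-off: 3 of 4.
- Share of follow-up analysed: 56/180 = 31%. Days outside: 180 − 56 = 124 (69%).

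**2. Position of the cut-off in the T-Guard arm.** Latest first dose is Day 3 (72 hours). Latest last dose is 3 + 14 = Day 17. Day 56 is at least 56 − 17 = 39 days after the last dose. On the nominal schedule (last dose Day 6) it is 50 days after.

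**3. Position of the cut-off in the ruxolitinib arm.** Because the earlier trial's median exposure (63 days) exceeds 56 days, at least half of that arm would still be on drug at Day 56 if the figure carried over. For the shape of time on drug, I assume an exponential distribution with median 63 days, with Weibull shapes 0.7 and 1.5 as a range.
- Exponential: λ = ln 2/63, so on drug at Day 56 = exp(−56λ) = 54%, and at Day 180 = 14%.
- Mean on-drug days 0-56 = (1 − 0.540)/λ = 41.8. Mean on-drug days 56-180 = (0.540 − 0.138)/λ = 36.5.
- Share of on-drug time within 180 days that falls after Day 56 = 36.5/(41.8 + 36.5) = 47%.
- Range over the Weibull shapes: 53-56% on drug at Day 56; 37-53% of on-drug time after Day 56.

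**4. Does the 63-day figure carry over?** Section 5.3.2 expects 40% mortality by Day 60. Of 123 per arm, 123 × 0.60 = about 74 would be alive. Half of the arm is about 62, so half on drug would need about 0.50/0.60 = 83% of survivors still taking it. That is high: only 101 of the 154 ruxolitinib patients in the earlier trial were Grade III-IV (sections 1.3.2.1 and 5.1.5), and section 2.5.3.4 ends study treatment when salvage therapy starts. If 30% of the arm continued (an illustrative assumption), the number would be about 0.30 × 123 = 37.

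**5. Other routes for toxicity after Day 56.**
- General adverse event reporting ends at Day 44 for ruxolitinib and 30 days after the last T-Guard dose (section 4.4.4).
- Events of special interest (TMA, CRS, CLS, myalgia, CK elevation, Grade 3 or higher cytopenias) are reported throughout follow-up. So are unanticipated SAEs, and SAEs judged related are reported after the general window (section 4.4.4).
- The DSMB receives adverse event and toxicity data at least annually, with no Day 56 limit (section 5.3).
- Section 5.2.1.2 foresees a safety analysis with 100 participants followed for 180 days but does not state its content.
- In Chapter 5, the only event of special interest with its own by-arm analysis is TMA, estimated at Day 28 (section 5.8.7).

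These are collection and oversight routes. None is a specified by-arm summary of Grade 3-5 toxicities after Day 56.

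**The case against.** The strongest reply is that late harm is covered elsewhere. The cytopenias that make ruxolitinib toxicity a concern are events of special interest in both arms through the whole of follow-up, and so are the named T-Guard toxicities. Overall survival and NRM are analysed to Day 180, as are treated CMV reactivation and EBV events; infections are analysed to Day 90. Day 56 is also a natural landmark, since it matches the planned minimum ruxolitinib period.

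Much of this stands, and it rules out several stronger readings. A reader might infer that later toxicity is collected and never reported; sections 4.4.4, 5.2.1.2 and 5.3 contradict that. A reader might infer that 69% of follow-up has no safety analysis; that is true only of the CTCAE toxicity summary. A reader might infer that late T-Guard harm is lost; the analysed window already covers at least 39 days after the last dose. Nor is it shown that most of the difference in exposure lies after Day 56: 39 to 50 days with ruxolitinib on and T-Guard off fall inside the window.

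What the reply does not supply is a by-arm table. The special-interest list omits, for example, Grade 3 hepatic or renal toxicity. Late SAEs are required only if judged related or unanticipated, and relatedness is judged by investigators who know the treatment. DSMB review is oversight, not a trial result.

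**Conclusion.** The mismatch holds. Toxicities are recorded to Day 180, the only specified toxicity endpoint and by-arm analysis stop at Day 56, and three of four scheduled recordings have no pre-specified summary. The omission falls mainly on toxicity during continuing ruxolitinib. Its size depends on how many participants continue: at least half of the arm if the earlier trial's median applies, plausibly fewer in Grade III-IV disease, and about 37 participants under the illustrative 30%. The 37-53% share of on-drug time after Day 56 rests on the same median and on assumed distribution shapes.

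This is a gap in the safety summary that is worth closing. It does not mean that safety data are withheld, and it does not invalidate the Day 56 comparison.

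**What to change.** In sections 3.4.2.10 and 5.6.12, keep the Day 56 tabulation and comparison unchanged. Add a descriptive tabulation of Grade 3-5 toxicities by arm for Days 57-180 and cumulatively to Day 180. Show the number alive at the start of each period and time on ruxolitinib. State the look-back period of the Day 70, 90 and 180 forms, which the documents do not give. If the sponsor prefers not to add the table, the plan should say why the later forms are collected.

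Do not add a formal Day 180 test. A binary logistic model over a period with heavy mortality ignores death as a competing event, and the Day 57-180 groups are no longer the randomized groups because they are conditioned on survival. Salvage therapy further blurs attribution. A note to this effect should accompany the table.

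The cost is SAP wording and one extra descriptive table from forms already scheduled. Time on ruxolitinib should be available from the start and stop dates captured for immunosuppressants (section 4.3.2), provided that ruxolitinib after Day 56 is recorded there; this should be confirmed. Alpha, sample size and treatment are unaffected.
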